3.3.4 Interviewer-administered asthma control questionnaire (ACQ-IA)

The change from baseline in ACQ-IA score, obtained at all post-baseline visits as indicated on Table 1 of the CSP will be used as a secondary variable to assess the effect of benralizumab on asthma symptoms and other asthma control metrics.

The ACQ-IA is a 6-item assessment comprised of 6 patient-reported items: 5 symptoms (night-time waking, symptoms on waking, activity limitation, shortness of breath, and wheezing) and use of short-acting β 2 agonist (SABA) over the previous week using a 7-point scale (0 = no impairment; 6 = maximum impairment). The ACQ-IA score is calculated by taking the mean of the 6 equally weighted items.

The ACQ score range is 0 (well controlled) to 6 (extremely poorly controlled).

The estimated threshold indicating poor asthma control is an ACQ-IA score ≥ 1.25 in patients ages 6 to 17 years ([Nguyen et al 2014](#), [Juniper et al 2006](#), [Juniper et al 2005](#)). The estimated minimal clinically important difference is 0.5 ([Juniper et al 2010](#))

The questionnaire will be completed at the study centre during every study visit except Visit 3 on Day 1 as indicated in Table 1 of CSP.

Other variables based on ACQ-IA to be reported at each time point include:

1. ACQ-IA responder (Yes=1/No=0):

- Responder: Change from baseline ACQ-IA score ≤ -0.5
- Non-responder: Change from baseline ACQ-IA score > -0.5 .

2. ACQ-IA response (Improved/No Change/Deterioration):

- Improvement: Change from baseline ACQ-IA score ≤ -0.5
- No change: $-0.5 < \text{Change from baseline ACQ-IA score} < 0.5$
- Deterioration: Change from baseline ACQ-IA score ≥ 0.5

3. Subject's asthma control as measured by ACQ-IA score:

- Well controlled: ACQ-IA score ≤ 0.75
- Partly controlled: $0.75 < \text{ACQ-IA score} < 1.25$
- Not well controlled: ACQ-IA score ≥ 1.25 .

3.3.5 Global Impression of Change

Clinician global impression of change (CGIC) and interviewer-administered patient global impression of change (PGIC-IA) instruments are used for an overall evaluation of response to treatment, conducted separately by the Investigator and by the patient administered by trained individuals, using a 7-point scale: 1=Very Much Improved; 2=Much Improved; 3=Minimally Improved; 4=No Change; 5=Minimally Worse; 6=Much Worse; and 7=Very Much Worse.

The Investigator (clinician) and the patient will be asked to rate the degree of change in the overall asthma status compared to the start of study treatment visit. The questionnaire will be completed by the patients and clinicians at Week 16 (Part A), and Weeks 24, 32, and 48 (Part B).

Patients will also be categorized according to the following responses post-baseline, separately for CGIC and PGIC:

- Very much improved, much improved, minimally improved \rightarrow 'Improved'
- Very much improved, much improved \rightarrow 'Much improved'
- Very much improved \rightarrow 'Very much improved'

Agreement between CGIC and PGIC-IA will be assessed at each visit, where agreement is achieved when both the patient and clinician provide the same response (e.g., if both the patient and clinician indicate a response of 1 (very much improved) at a particular visit, agreement is achieved for that visit). Agreement will also be assessed for categorized responses at each visit.

An interviewer administered PGIC (PGIC-IA) will be used in this study to help the child understand what is being asked. The PGIC-IA will be administered by trained individuals according to standardized instructions to help the child understand the question and response options. Help from caregivers/parents is sought only as a last resort. The PGIC-IA will be completed at the study centre at Visits 9, 10, 11 and 13 (CSP table 1).

3.3.6 Safety outcome variables

The following safety data will be collected: reported AEs (including SAEs), haematology, clinical chemistry, urinalysis, 12-lead electrocardiogram (ECG), physical examination and vital signs.

All safety measurements will use all available data for analyses, including data from unscheduled visits and repeated measurements.

Change from baseline to each post-treatment time point where scheduled assessments were made will be calculated for relevant measurements. AEs will be summarised by means of descriptive statistics and qualitative summaries.

No safety data will be imputed. The handling of partial/missing dates for AEs is detailed in [Appendix I](#).

3.3.6.1 Adverse events (AEs)

Adverse events (including SAEs) experienced by the patients will be collected throughout the entire study and will be coded by the AstraZeneca designee using the latest version of the Medical Dictionary for Regulatory Activities (MedDRA).

Adverse event data will be categorized according to their onset date into the following study periods:

- AEs in the on-study period, defined as:

date of first dose of IP \leq AE onset date \leq study completion or withdrawal date.

- *AEs in the pre-treatment period (screening period) are defined as those with onset before the day of first dose of study treatment.* If any subject is re-screened, the latest available screening will be used for this purpose

If the AE has a completely missing (and unresolvable) onset date, then the AE will be assumed to be treatment-emergent, unless the end date indicates unambiguously that the AE resolved before treatment started. If the AE has a partially missing (and unresolvable) onset date, then the AE will also be assumed to be treatment-emergent, unless either the end date

indicates unambiguously that the AE resolved before treatment started, or the partial onset date is in the month/year prior to start of treatment.

3.3.6.2 Laboratory variables

Samples for determination of clinical chemistry, haematology, virology and urinalysis parameters will be taken at the times detailed in the Table 1 of the CSP and assessed in a central laboratory. The parameters outlined in Table 8 of the CSP will be collected.

Changes in haematology and clinical chemistry variables between baseline and each post-baseline assessment will be calculated. The change from baseline is defined as the post-baseline value minus the baseline value. There will be no imputation for missing values. For values recorded with a leading greater than or less than ('>', '<') symbol, the reported numeric value will be used for analysis and the value with the symbol will be included in the listings, unless otherwise specified. For example, a value of <0.01 will be analyzed as 0.01 and listed as <0.01.

The investigator will assess the available lab results with regards to clinically relevant abnormalities. Absolute values will be compared to the relevant reference range and classified as low (below range), normal (within range or on limits) or high (above range). The central laboratory reference ranges that will be used will follow the most recent version of the AZ standard reference ranges and unit conversion external data. All absolute values falling outside the AZ provided reference ranges will be flagged in the listings. These classifications will also be used for shift tables.

Urinalysis data will be categorised as negative (0), positive (+), or strongly positive (++, +++, or >++) at each timepoint.

For the purpose of shift tables, baseline will be defined as specified in section 3.1.1. Maximum or minimum value post-baseline will be calculated over the entire post-baseline period.

For the liver function tests: aspartate aminotransferase (AST), alanine aminotransferase (ALT), alkaline phosphatase and total bilirubin (TBL), the multiple of the central laboratory upper limit of the normal (ULN) range will be calculated for each data point:

Multiple = Value / ULN,

i.e. if the ALT value was 72 IU/L (ULN 36) then the multiple would be 2.

Patients who meet any of the following criteria at any point during the study will be flagged:

- AST \geq 3x ULN
- ALT \geq 3x ULN
- TBL \geq 2x ULN

3.3.6.3 Vital signs

Vital signs such as systolic blood pressure, diastolic blood pressure, pulse rate, weight, height, Body mass index (BMI) and body temperature will be assessed. The assessment will be conducted while sitting with a completely automated device with a calibrated manometer using an appropriate pediatric cuff and in accordance with the visit schedule provided in Table 1 of the CSP.

Changes in the vital signs variables between baseline and each subsequent scheduled assessment will be calculated. Absolute values will be compared to the given reference ranges ([Table 2](#) and [Table 3](#)) and classified as low (below range), normal (within range or on limits) or high (above range). All values (absolute) falling outside the reference ranges will be flagged in the listings.

Table 2: Vital signs reference ranges for age 6 -11 years

Parameter	Standard Units	Lower Limit	Upper Limit
Diastolic Blood Pressure	mmHg	57	80
Systolic Blood Pressure	mmHg	97	120
Pulse Rate	Beats/min	70	110
Body Temperature	Celsius	35.5	37.5
Weight	kg	15	NA
Height	cm	NA	NA

Table 3: Vital signs reference ranges for age 12 -14 years

Parameter	Standard Units	Lower Limit	Upper Limit
Diastolic Blood Pressure	mmHg	64	83
Systolic Blood Pressure	mmHg	110	131
Pulse Rate	Beats/min	55	105
Body Temperature	Celsius	35.5	37.5
Weight	kg	15	NA
Height	cm	NA	NA

BMI will be calculated from the height and weight as follows:

$$\text{BMI (kg/m}^2\text{)} = \text{weight (kg)} / (\text{height (m)})^2$$

3.3.6.4 ECG

A 12-lead ECG will be obtained as outlined in Table 1 of the CSP using the site's own ECG machines after the patient has rested in the supine position for at least 10 minutes.

The outcome of the investigator's overall ECG evaluation will be recorded as normal/abnormal in the CRF and with any abnormalities recorded as not clinically significant or clinically significant. Changes from baseline in continuous 12-lead ECG variables will be calculated at relevant visits as specified in [Table 1](#).

3.3.6.5 Physical examination

A complete physical examination will be performed and include an assessment of the following: general appearance, respiratory, cardiovascular, abdomen, skin, head and neck (including ears, eyes, nose, and throat), lymph nodes, thyroid, musculo-skeletal (including spine and extremities), and neurological systems.

A brief physical examination will include the following: general appearance, respiratory, cardiovascular, and abdomen systems.

Complete and brief physical examinations will be performed at time points specified in CSP Table 1. Baseline data will be collected prior to first dose and any new finding(s) or aggravated existing finding(s), judged as clinically significant by the investigator or designee, will be reported as an AE.

3.3.7 Exploratory outcome variable

3.3.7.1 Annualised asthma exacerbation rate

For this study an asthma exacerbation is defined by a worsening of asthma requiring the use of systemic corticosteroids (or an increase in oral steroid dose for those already on systemic corticosteroids) and/or an emergency department (ED) visit requiring use of systemic corticosteroids and/or an in-patient hospitalization due to asthma.

The start of an exacerbation is defined as the start date of systemic corticosteroids or of an increase in oral steroid dose, date of ED requiring systemic corticosteroids, or date of hospital admission due to asthma, whichever occurs earlier. The end date of an exacerbation is defined as the last date of systemic corticosteroids or of an increase in oral steroid dose, date of ED, or date of hospital discharge, whichever occurs later.

If less than 7 days have elapsed since the end date of an asthma exacerbation and the start date of a new asthma exacerbation, the second event will be considered a relapse of the prior asthma exacerbation and will be recorded in the eCRF as the same exacerbation event.

Asthma exacerbation information will be collected with a recall period of ‘since the last scheduled visit’.

Information collected for asthma exacerbation will include in-patient hospitalizations, number of days in the hospital, and ED visits collected by the investigator/authorized delegate at each visit (as shown in table 1 of the CSP) and recorded in the eCRF. Asthma-related hospitalization and ED visit information will be collected with a recall period of ‘since the last scheduled visit’.

Time to first asthma exacerbation is the time from first IP dose to the first asthma exacerbation and is derived as follows:

$$\text{Start date of first asthma exacerbation} - \text{Date of first IP dose} + 1.$$

The time to first asthma exacerbation for patients who do not experience an asthma exacerbation during the treatment period will be censored at EOT visit (Week 48) for patients who complete study treatment. Patients who discontinue study treatment or are lost to follow-up before EOT visit will be censored at the last visit date after which an exacerbation could not be assessed.

The annualised asthma exacerbation rate (AAER) is an exploratory variable and will be calculated using the time-based risk approach as:

$$\text{AAER} = 365.25 * \text{Total number of exacerbations} / \text{Total duration of at risk on-treatment period (days)}.$$

4 ANALYSIS METHODS

4.1 General principles

The statistical analyses will be performed by IQVIA under the direction of the Biostatistics Group, AstraZeneca. The data analyses will be conducted using SAS® System (SAS Institute Inc., Cary, NC), Version 9.4 or higher. All analyses will be performed according to AstraZeneca standard operating procedures unless otherwise stated.

No formal statistical hypotheses will be tested in this study.

For PK related data summaries for patients aged 6 to 11 years will be presented in tabular format by treatment/weight groups (benralizumab ^{CCR} mg in patients < 35 kg at screening and benralizumab ^{CCR} mg in patients \geq 35 kg at screening). Up to 3 Japanese patients aged 12 to 14 years will be enrolled and listed for PK related data. Additional summaries for non-PK related data for patients aged 6 to 11 years, and aged 6 to 14 years overall will be provided.

Descriptive statistics on continuous data will be summarised by treatment/weight group including number of patients with available data (n), arithmetic mean (Amean), standard deviation (SD), median, minimum value and maximum value (unless stated otherwise) for non-PK data. Geometric mean (Gmean) and geometric coefficient of variation (gCV%) will also be produced for log-transformed data including PK concentration data. The Amean, median, Gmean and gCV% will be presented with one more decimal place than the raw data. The SD will be presented with two more decimal places than the raw data. In general, minimum and maximum values will have the same number of decimal places as the raw data except specified otherwise (see section 4.2.5.1 for PK parameters).

Gmean is calculated as $\exp[\mu]$, where μ is the mean of the data on a logarithmic scale.

gCV% is calculated as $100 \sqrt{[\exp(s^2) - 1]}$, where s is the SD of the data on a log scale.

Categorical data will be summarised by treatment/weight group using the number and percentage of patients in each category and the percentages will be rounded to 1 decimal place. Percentages will be calculated using the number of patients within each treatment/weight group and overall as the denominator.

When assessing minimum/maximum during the study, all assessments, including unscheduled/repeated assessments will be used. For analysis assessing change from baseline, only patients with both baseline and at least 1 post-baseline measure will be included. Unless otherwise specified, no algorithm for missing data imputation will be employed.

Although the study is conducted in two parts, Part A and Part B for 48 weeks of treatment period, the analysis of the study outcome variables will be analysed altogether not separately

by part and will include all data captured during screening period of up to 28 days and a treatment period of 48 weeks, and a safety follow-up visit at Week 52. A patient who withdraws prior to the last planned observation in a study period will be included in the analyses up to the time of discontinuation, as appropriate.

Medical and surgical histories will be recorded using the latest version of medical dictionary for regulatory activities (MedDRA) Preferred Term (PT) within the System Organ Class (SOC) level of MedDRA.

Data listings will be sorted by patient number. Summaries by visit will include baseline.

4.2 Analysis methods

No formal analyses will be performed for this study. Demographic and other baseline characteristics, exposure, safety and tolerability data and PK will be summarised and listed.

4.2.1 Patient disposition

Patient disposition will be summarised using all enrolled subjects (all patients set) who signed the informed consent form, including screening failures.

The number and percentage of patients will be presented by the following categories: assigned study treatment, not assigned study treatment (including reason), received study treatment, did not receive study treatment (including reason), completed treatment, discontinued from study treatment (including reason), completed study, and prematurely withdrawn from study (including reason). Study discontinuation reasons are detailed in CSP Section 7.1. Also subjects who completed study will be summarized by subjects who completed IP and study, and subjects who discontinued IP but completed study assessments.

Reasons for not having received study treatment, discontinuation of IP and prematurely withdrawing from study will also be listed including the study day of treatment discontinuation.

Important protocol deviations will be summarised by treatment/weight group and listed for the safety analysis set.

The number and percentage of patients included and excluded from each analysis set will be summarised by treatment/weight group, including the reason for exclusion from each analysis set. Patients in the safety analysis set excluded from the PK analysis set, including reason, will also be listed.

4.2.2 Demography data and patient characteristics

Demography data such as age (years), gender, race, and ethnicity will be summarized by treatment/weight group and for all patients in the safety analysis set. Age will be derived from

the date of informed consent-date of birth, rounded down to the nearest integer. For patients in country where date of birth is not recorded the age as recorded in the eCRF will be used.

Various baseline characteristics will also be summarized by treatment/weight group and for all patients in the safety analysis set. These include patient characteristics (weight, height and BMI), maintenance asthma medications, maintenance inhaled corticosteroids (ICS) medications, maintenance oral corticosteroids (OCS) use, medical and surgical histories, spirometry lung function data at screening such as FEV₁, FEV₁/FVC, blood eosinophil count at baseline, and respiratory disease characteristics including asthma duration, age at onset of asthma, the number of exacerbations in the previous 12 months, and the number of exacerbations requiring hospitalizations in the previous 12 months.

Medical and surgical histories will be summarized by MedDRA Preferred Term (PT) within System Organ Class (SOC) level on MedDRA.

4.2.3 Prior and concomitant medications

All medications will be classified by the AstraZeneca designee using the anatomical therapeutic chemical (ATC) classification system according to the latest version of the World Health Organisation (WHO) Drug Dictionary will be presented by treatment/weight group using the safety analysis set and will be categorised as:
prior medications and concomitant medications.

4.2.3.1 Prior medications

A medication will be regarded as prior if it was stopped on or before the date of first dose of study treatment (*medication stop date <= date of first dose of study treatment*).

4.2.3.2 Concomitant medications

A medication will be regarded as concomitant if the start date is on or after the first IP dose date, but prior to the end of study period (date of first dose of study treatment <= medication start date <= study completion or withdrawal date), or if it started on or prior to the first IP dose date and was ongoing after the first IP dose date.

The handling of partial/missing dates for prior/concomitant medications is detailed in [Appendix I](#).

The number and percentage of patients taking maintenance asthma medications such as ICS/long acting beta agonist (LABA) fixed dose combinations, at baseline will be summarised. Those patients taking ICS and/or OCS at baseline, the converted dose units will also be summarised. The number of patients treated with ICS at baseline will be summarised by ATC code and preferred term, with total daily dose (non-converted) at baseline summarised for each preferred term. A similar summary will be prepared to summarize total daily dose of OCS at baseline

Disallowed medications will include medications defined as prohibited according to Section 6.6 of the CSP. They will be defined following a physician review (prior to database lock) of the unique combinations of Anatomical Therapeutic Chemical (ATC) code classifications and generic terms captured.

Separate tables will be presented for all allowed and disallowed medications received during each of the following periods: pre-treatment and on study period respectively.

Prior and concomitant medications will be listed for the safety analysis set, including allowed and disallowed medications.

4.2.4 Study treatment

4.2.4.1 Exposure

Investigational product total treatment duration (days) is defined as the date of last dose minus the date of first dose plus 1 day.

Exposure to IP will be calculated in days as:

Exposure (days) =Last dose date of IP-first dose date of IP+1,

and will be summarized by treatment/weight group for the safety analysis set.

The date of all IP administrations, and all missed doses will be listed using the safety analysis set. Reason for missed dose will also be listed.

Exposure data will be summarised and listed for the safety analysis set.

4.2.4.2 Compliance

Study treatment compliance will be summarized descriptively by treatment/weight group for the safety analysis set and will be calculated as:

Treatment compliance (%) = (Total doses administered/total doses expected up to last treatment date) x 100%.

Patients who received no study treatment will have zero compliance.

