| Section 8.2.4 Electrocardiograms | Clarification that ECG readings can be stored as physical copies in subject's source files. | Clarification | Non-substantial |

| Section # and Name | Description of Change | Brief Rationale | Substantial/ Non-substantial |
|--|--|--|---------------------------------|
| Section 8.4.6 Medical device deficiencies; Section 8.4.6.1 Time period for detecting medical device deficiencies; Section 8.4.6.2 Follow-up of medical device deficiencies; Section 8.4.6.3 Prompt reporting of medical device deficiencies to Sponsor; Section 8.4.6.4 Regulatory reporting requirements for device deficiencies; Appendix G Medical device AEs, ADEs, SAEs, SADEs, USADEs and medical device deficiencies: definitions and procedures for recording, evaluating, follow-up, and reporting in medical device studies | New sections added to discuss device constituent deficiencies. | New sections to discuss device deficiencies in line with new EU/US regulations and CSP template. | Substantial |

Version 4.0, 01 July 2020

In this amendment to the protocol:

- Section 4.1.1 (Study conduct mitigation during study disruptions due to cases of civil crisis, natural disaster, or public health crisis), Section 8 (Study assessments and procedures), Section 9.7 (Sensitivity analyses), and Appendix B:
 - New text was added to clarify how the study could continue in the event of a serious disruption, including details of mitigations that could be employed to ensure study continuity.
- Section 5.1 (Inclusion criteria):
 - The duration of mandatory contraception use during the study was updated: contraception to be used for 12 weeks (rather than 4 months) after the last dose of IP.

- Section 6.3.3 (After investigational product administration) and Section 8.4.4 (Management of investigational product-related reaction):
 - The minimum observation time (for the appearance of acute drug reactions) following investigational product administration was shortened to 1 hour.
- Section 6.6 (Concomitant therapy):
 - The study period during which the use of live attenuated vaccines was prohibited was updated: live attenuated vaccines use prohibited for 12 weeks (rather than 4 months) after the last dose of IP.
- Section 7.1 (Discontinuation of study treatment):
 - Criteria for discontinuation due to missed doses of IP updated to specify applicable to Part A only.
- Section 8.1.1.2 (Spirometry technique)

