
Study Period:

Estimated date of first patient enrolled: November 2019

Estimated date of last patient completed: September 2022

Number of Subjects:

Approximately 30 evaluable patients aged 6 to 11 years will be treated with benralizumab across the 2 combined weight strata, with a minimum of 8 patients in each stratum. Up to 3 additional Japanese patients aged 12 to 14 years will be enrolled.

Treatments and treatment duration:

Patients aged 6 to 11 years will receive either [redacted] mg or [redacted] mg of benralizumab (MEDI-563) based on baseline body weight for SC injection and the dose for each patient will not change during the study. Patients aged 12 to 14 years will receive [redacted] mg of benralizumab (MEDI-563) for SC injection during the study. Study treatment will be provided in an accessorised pre-filled syringe. Each syringe will be labelled in accordance with Good Manufacturing Practice (GMP) Annex 13 and per country regulatory requirement.

In Part A, patients will receive 4 doses of study treatment (the first 3 doses every 4 weeks and the fourth dose 8 weeks after) depending on body weight. In Part B, 8 weeks after completing Part A, patients will receive an additional 3 doses of study treatment every 8 weeks (Q8W). The total duration of the study for most patients will be up to 56 weeks and will include a screening period of up to 28 days and a treatment period of 48 weeks, and a safety follow-up visit at Week 52. The total duration of the study may be longer if the screening period is extended.

Data Safety Monitoring Board:

A Data Safety Monitoring Board (DSMB) will oversee specific aspects of this study.

Statistical methods:

The sample size is not based on a formal sample size calculation. A sample size of 30 evaluable patients aged 6 to 11 years, with a minimum of 8 patients in each weight stratum, was chosen to provide sufficient data across the dosing and weight categories for PK parameter estimations using noncompartmental analysis (NCA) criteria assuming 30% for percent of coefficient of variation (CV%). Evaluable patients are defined as those patients with at least 3 post-first investigational product (IP) dose PK assessments above the lower limit of quantification. A cohort of up to 3 Japanese patients aged 12 to 14 years has been added following discussion with the PMDA.

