7 DISCONTINUATION OF TREATMENT AND SUBJECT WITHDRAWAL

7.1 Discontinuation of study treatment

Patients may be discontinued from IP in the following situations. Note that discontinuation from study treatment is NOT the same thing as a complete withdrawal from the study.

- Patient or guardian decision. The patient is at any time free to discontinue treatment, without prejudice to further treatment
- Adverse event
- Severe non-compliance with the CSP
- Eligibility requirement found not to be fulfilled
- Positive pregnancy test at any time during the study
- Lost to follow-up
- Development of any study specific criteria for discontinuation:
 - Anaphylactic reaction to the IP requiring administration of epinephrine

- Development of helminth parasitic infestations requiring hospitalization
- If 2 consecutive doses of IP are missed or more than 2 scheduled doses of IP are missed during Part A dosing
- An asthma-related event requiring mechanical ventilation.

See [Table 1](#) for data to be collected at the time of treatment discontinuation and follow-up and for any further evaluations that need to be completed.

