4.2.6 Pharmacodynamic variables

4.2.6.1 Change in Eosinophils count

Peripheral blood eosinophils values and changes from baseline at each visit will be summarized using descriptive statistics for each treatment/weight group based on safety

analysis set. For DXD, only the PD samples collected within one dosing cycle after last dose will be included in the summary statistics during treatment period.

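### The SAP's compliance percentage leaves out doses missed at the end of the schedule, so a child not recorded as discontinued can score 100% on 5 of 7 planned doses

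*SAP*

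**What the plan says.** SAP 4.2.4.2 summarises compliance by treatment/weight group in the safety analysis set, using "Treatment compliance (%) = (Total doses administered/total doses expected up to last treatment date) x 100". The SAP does not define the last treatment date. The section just before it, SAP 4.2.4.1, fixes the end of treatment at the last dose: "Investigational product total treatment duration (days) is defined as the date of last dose minus the date of first dose plus 1 day".

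The Protocol Synopsis sets the schedule. "In Part A, patients will receive 4 doses of study treatment", at Day 0 and Weeks 4, 8 and 16. Part B adds three more, at Weeks 24, 32 and 40.

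SAP 3.1.3 runs the on-treatment period from the first dose to the end-of-treatment visit, or to the early discontinuation (DXD) visit for children who stop early.

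For eosinophils, SAP 4.2.6.1 limits time since dosing for DXD samples alone: "only the PD samples collected within one dosing cycle after last dose will be included". Samples from scheduled visits carry no such condition. SAP 3.1.4 assigns them to visits by study day.

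**The concern.** The denominator stops growing at the last dose given. A skipped dose lowers compliance only if a later dose follows it; a skipped run at the end of the schedule does not count. The measure therefore cannot show late cessation in a child who is still recorded as on treatment. It can also give a child with fewer doses a higher figure than a child with more.

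The SAP's two definitions also diverge for such a child. Under SAP 3.1.3 the child is on treatment to Week 48, while the compliance count ended weeks earlier. A reader who uses the compliance table to judge whether the long-term data reflect the planned regimen would see full dosing.

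**Working it through.** **Inputs.** Planned doses (Protocol Synopsis): Weeks 0, 4, 8, 16, 24, 32 and 40, so 4 + 3 = 7. SAP compliance = doses given / doses scheduled up to and including the last dose given. Comparator = doses given / 7. The documents give no compliance figure to reproduce.

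**Children who attend Week 48 and are not recorded as discontinued:**

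| Doses missed | Given | Expected to last dose | SAP compliance | Share of 7 planned |
|---|---|---|---|---|
| Week 8 only | 6 | 7 | 85.7% | 85.7% |
| Weeks 24 and 32 | 5 | 7 | 71.4% | 71.4% |
| Week 40 only | 6 | 6 | 100% | 85.7% |
| Weeks 32 and 40 | 5 | 5 | 100% | 71.4% |
| Weeks 24, 32 and 40 | 4 | 4 | 100% | 57.1% |
| Weeks 16 to 40 | 3 | 3 | 100% | 42.9% |
| Weeks 4, 32 and 40 | 4 | 5 | 80.0% | 57.1% |

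Rows 2 and 4 have the same number of doses but differ by 28.6 points, only because of where the gap falls. The last row shows that an earlier gap removes the 100% score but not the overstatement.

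**Group level.** Suppose one child misses Weeks 32 and 40 and all others take 7 doses. In a stratum of 8 the mean is 100% by the SAP formula, against (7 × 100 + 71.4)/8 = 96.4% of planned doses. In a stratum of 15 it is 100% against (14 × 100 + 71.4)/15 = 98.1%.

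**What other outputs show.** Exposure is last dose minus first dose plus 1. For the child who misses Weeks 32 and 40 it is 168 + 1 = 169 days, against 280 + 1 = 281 for full dosing. The shortfall is visible there, but not as a count of missed doses.

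**Eosinophil samples.** Doses are eight weeks apart from Week 8 onward, so one cycle is 56 days, or 63 with the 7-day visit window.

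- Weeks 32 and 40 missed: last dose Day 168, Week 48 sample Day 336, gap 168 days.
- Only Week 40 missed: last dose Day 224, gap at Week 48 = 112 days.
- Week 16 missed after a Week 8 dose: last dose Day 56, Week 24 sample Day 168, gap 112 days. If Week 16 was given, the Week 24 sample is on cycle.

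Each off-cycle gap exceeds 63 days, yet the sample enters the scheduled-visit summary. One such child is 1/8 = 12.5% of a minimum-size stratum, or 1/15 = 6.7% of an average one (30 children in two strata).

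**The case against.** The strongest reply is that the formula measures adherence while on treatment, and that persistence is reported elsewhere. SAP 4.2.4.1 summarises exposure by group and lists every administration and every missed dose with its reason. SAP 4.2.1 tabulates treatment completion and discontinuation, and summarises and lists important protocol deviations. With about 30 children, a careful reader could find late missed doses. Compliance feeds no endpoint and the study is descriptive throughout. All of this stands, and it limits the consequence. It does not make the compliance figure correct: the missed doses are only listed, disposition counts recorded discontinuations and not skipped doses, and no table of doses received is specified.

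It can also be said that the eosinophil route is narrow. Protocol 7.1.1 sends children who stop early to a DXD visit within 4 weeks of the last dose, after which haematology is no longer required. The route therefore mainly needs a child who skips the last doses, is not recorded as discontinued and attends Week 48. That is possible under the text, but nothing shows that it happened. Keeping all observed samples in the main summary is a legitimate choice.

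A reader might also infer that the plan is defective because Part B has no numeric missed-dose limit. The criterion in Protocol 7.1 reads "If 2 consecutive doses of IP are missed or more than 2 scheduled doses of IP are missed during Part A dosing", and the amendment summary records "Criteria for discontinuation due to missed doses of IP updated to specify applicable to Part A only". The restriction was deliberate, "Severe non-compliance with the CSP" remains a general ground, and no passage contradicts another. Whether Part B needs such a limit is a clinical matter and forms no part of this point.

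**Conclusion.** The point holds as a defect in a descriptive table. On the natural reading of the last treatment date, end-of-schedule omissions by a child not recorded as discontinued never lower compliance. The figure is overstated by 14.3 points for one missed final dose (100 − 85.7), 28.6 for two (100 − 71.4) and 42.9 for three (100 − 57.1), given no earlier gap. If the term was meant as the scheduled end of dosing, the problem disappears, but the SAP does not say so. The zero-compliance clause in SAP 4.2.4.2 is no safeguard, because every child in the safety set has had at least one dose.

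A reader might go further and conclude that the primary eosinophil result is biased. The documents do not support that. They allow off-cycle Week 24 or Week 48 samples into the summary, but they give no eosinophil recovery time and no evidence of how many children would be affected. The 12.5% share is the minimum-stratum case, and the size of any effect on the counts is unknown. A supportive display is justified; replacing the all-data summary is not.

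**What to change.** In SAP 4.2.4.2, define the denominator as doses scheduled up to the end of the on-treatment period in SAP 3.1.3, or up to the recorded date of IP discontinuation for children who stop. The child who misses Weeks 32 and 40 and attends Week 48 then scores 5/7 = 71.4%.

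This alone is not enough. A child who formally discontinues after Week 8, before Week 16 is due, still scores 3/3 = 100%. So also tabulate the number of doses received (1 to 7) by treatment/weight group.

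In SAP 4.2.6.1, keep the all-data eosinophil summary as the main one. Add a supportive display of Weeks 24 and 48 with and without samples taken more than one dosing cycle plus the visit window after the last dose.

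The cost is a few sentences of SAP text and minor programming on dose dates already collected. The downsides are that reported compliance may be lower, and that one extra table and the supportive display are needed.
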